6.4 STUDY INTERVENTION COMPLIANCE

Assessment of adherence to the assigned study drug will provide clinic staff a means to identify participants having problems with adherence. Adherence will be assessed by:

- Counts of capsules in the participant's returned medication bottle at the end of the trial
- Conducting a brief, structured interview, in which the study coordinator will assist the participants to identify problems in taking the study drug and to estimate adherence to the prescribed medicine since their previous visit during the trial.

These assessments will guide the consideration of strategies to improve adherence and to assess adherence at the end of the trial.

6.5 CONCOMITANT THERAPY

For this protocol, a prescription medication is defined as a medication that can be prescribed only by a properly authorized/licensed clinician. Medications to be reported in the Case Report Forms (CRF) are concomitant prescription medications, over-the-counter medications and supplements.

Medication histories are collected at enrollment and at each follow-up visit. The participant is requested to bring all medication and supplement bottles (prescription and non-prescription) or a photo of each bottle to the clinic visit.

The drug interaction/contraindication list from the buspirone manufacturer's drug label (package insert) will be the definitive source of identifying which concomitant pharmaceuticals and herbal supplements should be considered in determining eligibility for this study and which medications can be safely taken with buspirone during the trial.

Medications known to interact with buspirone hydrochloride (buspirone) are excluded from use during the trial. These include:

- MAO inhibitors, such as phenelzine, linezolid, isocarboxazid, methylene blue, moclobemide, phenelzine, procarbazine, rasagiline, safinamide, selegiline, and tranylcypromine
- The blood thinner warfarin (Coumadin)
- Haloperidol
- Benzodiazepines
- Drugs used to treat seizures, such as phenytoin (Dilantin) and carbamazepine (Tegretol)

In addition, using buspirone with any of the following medicines may cause an increased risk of certain side effects. These medications are selective serotonin reuptake inhibitors (SSRIs)(e.g., fluoxetine, nefazodone and trazodone (Oleptro)), and tricyclic antidepressants (TCA; e.g., amitriptyline/nortriptyline, trazodone). Some drugs interact with buspirone to affect the clearance rate of buspirone, including azole antifungals (e.g., itraconazole, ketoconazole), some antibiotics (including erythromycin, rifampin), nefazodone, cimetidine, ritonavir, diltiazem, verapamil, and certain anticonvulsants (e.g., phenytoin, phenobarbital).

Drugs with the possibility of a serious adverse event or disruption of the clearance rate have been listed as exclusions to the study. The treating physician will assess each participant's medication profile both for study eligibility at screening and for ongoing safety during the trial, and participants will be excluded from randomization or have trial treatment discontinued on a case-by-case basis per local clinical judgment.

Participants will be questioned regarding any new medications at each visit and counseled by the study physician not to use drugs on the list of exclusions above, unless they are medically necessary. The study physician will decide whether suspension of the study medication is indicated.

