2.3 RISK/BENEFIT ASSESSMENT

2.3.1 KNOWN POTENTIAL RISKS

Risks of buspirone: Common buspirone side effects may include: headache; dizziness, tiredness, drowsiness, and lightheaded feeling; sleep problems (insomnia); nausea, upset stomach; blurred vision; nervousness or excitement, nonspecific chest pain; sore throat, nasal congestion, tinnitus; and rarely, tardive dyskinesia. Common drug interactions of buspirone include monoamine oxidase (MAO) inhibitors. Thus far, there is no direct evidence that buspirone causes physical dependence or drug-seeking behavior.

Interference with cognitive and motor performance: Studies indicate that buspirone hydrochloride tablets are less sedating than other anxiolytics and that it does not produce significant functional impairment. However, its central nervous system effects in any individual participant may not be predictable. Therefore, participants should be cautioned about operating an automobile or using complex machinery until they are reasonably certain that buspirone treatment does not affect them adversely. In general, because the effects of concomitant administration of buspirone with most psychotropic (CNS-active) drugs have either not been studied or validated, the concomitant use of psychotropic drugs and buspirone should be approached with caution.

While formal studies of the interaction of buspirone hydrochloride with alcohol indicate that buspirone does not increase alcohol-induced impairment in motor and mental performance, it is prudent to avoid concomitant use of alcohol and buspirone.

Potential for Withdrawal Reactions in Sedative/Hypnotic/anxiolytic drug-dependent participants:

Because buspirone hydrochloride tablets do not exhibit cross-tolerance with benzodiazepines and other common sedative/hypnotic drugs, it will not block the withdrawal syndrome often seen with cessation of therapy with these drugs. Therefore, before starting therapy with buspirone hydrochloride tablets, it is advisable to withdraw participants gradually from their prior treatment, especially participants who have been using a CNS depressant drug chronically. Rebound or withdrawal symptoms may occur over varying time periods, depending on the type of drug and its effective half-life of elimination.

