For assessment of study intervention adherence see Study Intervention Compliance, [section 6.4](#).

Management of Comorbid Conditions

Any participant's comorbid conditions, including diabetes, will be managed according to the best clinical practice or evidence-based practices by the site principal investigator with input from the participant's primary care physician (PCP), and with consideration for medications contraindicated for use with buspirone (listed in [section 6.5](#)). Most of the comorbid conditions will be treated by continuing the treatments already instituted by the participant's regular physicians; worsening of the condition will be treated by the PI according to best clinical practice along with the participant's regular physicians. If the physician determines that the participant's safety is at risk, the participant's study drug will be discontinued. For follow-up care, the physician will refer the participant to their PCP or a specialist, if needed, and also continue to follow the participant at the site.

A uniform set of practices to be applied by the GpCRC investigators in the care of these participants will be provided in the trial SOP (Standard of Care document), prepared by the GpCRC Steering Committee, including the

Study Medical Safety Officer, and in conjunction with the BESST PI. This document is based on accepted best clinical practice and guidelines from the American Gastroenterological Association, the American Neurogastroenterology and Motility Society, and the American College of Gastroenterology.

If a participant develops diabetes during the participant's participation in the trial and the physician determines the need for antidiabetic medication (e.g., because of lack of response to life style changes), the use of medications not contraindicated with buspirone will be recommended for the specialist to consider. Likewise, for other classes of drugs (anti-hypertensives or anti-depressants) that may be prescribed for a worsening comorbid condition, careful consideration must be given to whether there is a non-contraindicated treatment with buspirone that can be prescribed to the participant, with the ultimate decision being the participant's safety.

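### Section 6.5 bars MAO inhibitors during the trial, but if one becomes medically necessary, stopping study drug is left to the study physician rather than required

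*Combined protocol and SAP*

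**What the plan says.** Section 6.5 opens with a flat ban: "Medications known to interact with buspirone hydrochloride (buspirone) are excluded from use during the trial". MAO inhibitors head the list that follows, and linezolid and methylene blue are named among them.

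The ban is then relaxed. Participants are counselled "not to use drugs on the list of exclusions above, unless they are medically necessary", and the next sentence reads "The study physician will decide whether suspension of the study medication is indicated". The paragraph that closes the discussion of interacting drugs is similar: participants may "have trial treatment discontinued on a case-by-case basis per local clinical judgment".

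Elsewhere the protocol treats this class as one to keep away from buspirone:

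- Section 2.3.1: "Common drug interactions of buspirone include monoamine oxidase (MAO) inhibitors".
- Section 5.2 excludes anyone with MAO inhibitor use at entry or in the previous 30 days.
- Items 1 to 3 of the participant handout in Section 6.1.2 all concern MAO inhibitors. Item 1 forbids them. Items 2 and 3 ask for 2 weeks' separation in each direction unless a physician directs otherwise.

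**The concern.** An MAO inhibitor can be started for a reason unrelated to gastroparesis. Section 6.1.2 itself identifies linezolid as an antibiotic, so an outside prescriber could begin one mid-trial. At that point the participant holds a handout saying the two drugs should not be combined, while the site has a protocol saying the study physician decides whether to suspend study drug. The site rule is the looser of the two, for a class the protocol singles out.

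What is at stake is the safety of a small number of participants. A stop fixed in advance would take one decision away from individual judgment, as the protocol already does for pregnancy and major skin reactions.

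**Working it through.** The protocol states no figure on this point to reproduce. The main check is whether any provision makes the stop mandatory.

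**Provisions that could close the gap**

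| Section | What it provides | Does it require a stop when an MAO inhibitor is started? |
|---|---|---|
| 6.5 | The package insert "will be the definitive source of identifying which concomitant pharmaceuticals and herbal supplements should be considered", and also decides what can be taken safely with buspirone | No. It informs the decision but is not written as a stopping rule |
| 7.1 | Stop for a treatment-related adverse event of grade 3 or above, or for intolerance | No. It acts after an event or on intolerance |
| 7.2 | Lists a newly met exclusion criterion, and the participant's best interest, as reasons to discontinue or withdraw | No. The investigator *may* act, and the subject is withdrawal from the study |
| 8.2 | "If the physician determines that the participant's safety is at risk, the participant's study drug will be discontinued" | Only after the physician has made that determination |
| 8.2 | When a coexisting illness worsens and a new drug is needed: "careful consideration must be given to whether there is a non-contraindicated treatment with buspirone that can be prescribed to the participant" | No. It asks for alternatives to be considered |
| 6.3 | Unmasking in unforeseen situations, at the discretion of the site principal investigator | No. It concerns the treatment code |
| 6.1.2, items 1 to 5 | Forbid or separate MAO inhibitors; tell participants to report the trial and their medications | No. Addressed to the participant and dependent on reporting |

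For comparison, Section 8.2 fixes an immediate stop for pregnancy and for major skin reactions, and Section 6.3 repeats it for pregnancy. Section 2.3.1 expects such skin reactions to be infrequent, so rarity did not prevent a fixed rule there.

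**Illustrative exposure (buspirone arm)**

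Inputs: 10 mg three times daily (Section 6.1.2); ideal visit dates of day 14 and day 28 (Section 8.1.4).

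- Between scheduled reviews, with no report in between: 14 days × 3 = 42 capsules; 42 × 10 mg = 420 mg.
- If study drug continues to day 28 after an MAO inhibitor starts on day d: (28 − d) × 3 capsules.
  - d = 7: 63 capsules, 630 mg
  - d = 14: 42 capsules, 420 mg
  - d = 21: 21 capsules, 210 mg

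These are not maxima. Visit windows are contiguous around the ideal dates, and dosing runs to the week 4 electrogastrogram visit, which may fall after day 28. A bottle holds 120 capsules, which is 120 / 3 = 40 days of supply against the 28 × 3 = 84 capsules that 28 days require.

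**Cost of a mandatory stop to the treatment comparison**

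Input: the 0.5-point difference and 54 per group in Section 9.2. Assumption: 1 to 3 buspirone participants stop and lose the whole effect.

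- 1 of 54: 0.5 × 1/54 = 0.009 points (1.9% of 0.5)
- 3 of 54: 0.5 × 3/54 = 0.028 points (5.6% of 0.5)

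Some of these participants would be stopped by the study physician under the present wording anyway, so the added cost would be smaller.

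**The case against.** The strongest reply is that the plan has layered protection and has chosen clinical discretion on purpose. MAO inhibitors are barred at entry and during the trial, participants are warned, medications are reviewed at every visit, and the label is the reference. A licensed physician decides, and must stop study drug once safety is judged to be at risk. Section 7.2 gives a newly met exclusion criterion as a reason to act, which fits this event directly. Section 6.3 allows unmasking, Section 8.2 involves the primary care physician, and handout item 4 has the participant tell that physician the drug and dose. On this view an automatic stop for a rare event in a 4-week trial is a drafting preference.

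Much of that stands. A reader might infer that the protocol freely permits combined use, or that no one outside the trial would hear of the buspirone. The documents do not support either reading: the physician must make a decision, and there are routes for communication. What does not fall is the narrower point. Every layer ends in judgment or in participant reporting, none requires the stop, and no provision gives the study team the duty to inform the prescriber of the MAO inhibitor. The package insert is not part of the documents, so how far it constrains the physician cannot be judged here.

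**Conclusion.** The point holds as a participant-safety gap of modest weight: discretion is the protocol's stated rule for a class it otherwise bars, and that rule is looser than its own handout. It deserves correction because correction costs almost nothing.

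Limits on the conclusion:

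- The documents give no rate of MAO inhibitor starts and no measure of harm from the combination. Starts should be rare in 4 weeks with the class barred at entry.
- The capsule counts show what the wording leaves open under stated assumptions. A reader might take 14 days or 42 capsules as a ceiling; the visit windows and bottle size show that they are not.
- A reader might infer a threat to the trial's result. There is none: the primary analysis is unaffected by the present wording, and even the assumed 1 to 3 extra stops would shrink a 0.5-point difference by at most 0.028.

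One linked matter needs settling at the same time. Section 7.1 keeps participants who stop study drug in the study, but Section 7.2 lets the investigator withdraw someone who cannot receive buspirone for 7 days or who newly meets an exclusion criterion. A participant stopped for an MAO inhibitor could be withdrawn on either ground.

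**What to change.** 1. **Section 6.5, final sentence.** Replace with:

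   > If an MAO inhibitor (including linezolid or methylene blue) is prescribed or started, study drug must be stopped immediately and not restarted. Where clinically possible, the MAO inhibitor is delayed until 2 weeks after the last study dose. If it cannot be delayed, the study physician informs the prescriber of possible buspirone exposure, with unmasking under Section 6.3 if needed. For all other new medications, suspension of study drug remains the study physician's decision.

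2. **Section 6.5, sentence on case-by-case discontinuation.** Add the matching exception for MAO inhibitors.

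3. **Section 6.1.2, handout item 1.** Add:

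   > If one is prescribed to you, stop the study capsules and call the study clinic the same day.

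4. **Section 7.2.** State that stopping study drug for an MAO inhibitor is not by itself a reason to withdraw the participant from follow-up under the 7-day or exclusion-criterion items.

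The 2-week interval matches handout item 2, which can stay as it is. The cost is a protocol amendment and a reprinted handout. The downside is that a few participants, including some on placebo, stop study drug early. Sample size, visits and analysis do not change.

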6.5.1 RESCUE MEDICINE

If symptoms are severe and require further treatment during the trial, participants will be instructed to take rescue medications that they would usually take, such as prochlorperazine or ondansetron for nausea and vomiting, and acetaminophen, ibuprofen, hyoscamine or tramadol for abdominal pain.

7 STUDY INTERVENTION DISCONTINUATION AND PARTICIPANT DISCONTINUATION/WITHDRAWAL

Participants may withdraw voluntarily from the study or the PI may, for cause, discontinue a participant from the study. In addition, participants who discontinue the study medication will be encouraged to remain in the study for follow-up purposes, especially for safety and efficacy study outcomes. Study medication discontinuations and participant discontinuations/withdrawals from the study will be documented on case report forms, which capture the dates and the specific underlying reasons for discontinuations of study medications or participant discontinuations/withdrawals.

7.1 DISCONTINUATION OF STUDY INTERVENTION

If the participant develops a treatment-related CTCAE v5.0-defined adverse event (grade 3 or above) on the 10 mg dose, the study medication will be stopped after assessment by the site study investigator, who is a licensed physician. If in the view of the study investigator, the participant is intolerant of the medication, the participant will be withdrawn from the study medication, but will continue to be followed to the end of the trial.

Discontinuation from buspirone or placebo does not mean discontinuation from the study -- all remaining study data should be completed as indicated by the study protocol. If a clinically significant finding is identified after enrollment, the investigator or qualified designee will determine if any change in participant management is needed. If indicated, adverse event (AE) case report forms will be completed and entered into the study database.

The data to be collected at the time of study intervention discontinuation will include the following:

- Labs and anthropometrics at the prior visit or at the AE occurrence
- Study medication bottle numbers and documentation of capsule counts

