Treatment of side effects: During BESST, if a participant develops non-life threatening side effects that may be attributed to the study drug, the study drug will be stopped only if the participant so desires. If the participant chooses to no longer receive the study drug, the participant will continue to be followed in the trial, in keeping with the intention-to-treat paradigm. In the event of major dermatological reactions such as generalized urticaria, bullous rashes, exfoliative dermatitis, or Stevens-Johnson Syndrome, study drug will be discontinued immediately. Such skin reactions are expected to be infrequent adverse events.

Study visits: This study requires approximately 8 visits to the study center (up to 3 screening visits, randomization visit, and 4 post randomization visits) which may cause some inconvenience to some individuals.

Pregnancy: Since there may be unknown risks to pregnant women and their unborn children, potential participants who are breast feeding, pregnant, or planning to become pregnant will not be allowed to participate in BESST. Participants need to confirm to the best of their knowledge that they are not pregnant and if they become pregnant during the course of the study, they must notify the study investigator immediately and the study drug will be stopped. A urine pregnancy test is obtained at study enrollment and at each visit during study treatment for any females of child-bearing potential to help assure that the participant is not pregnant.

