7.2 PARTICIPANT DISCONTINUATION/WITHDRAWAL FROM THE STUDY

Participants are free to withdraw from participation in the study at any time upon written request.

An investigator may discontinue or withdraw a participant from the study for the following reasons:

- Pregnancy
- Significant study intervention non-compliance
- If any clinical adverse event (AE), laboratory abnormality, or other medical condition or situation occurs such that continued participation in the study would not be in the best interest of the participant
- Disease progression which requires discontinuation of the study intervention
- If the participant meets an exclusion criterion (either newly developed or not previously recognized) that precludes further study participation
- Participant is unable to receive buspirone for 7 days.
- The sponsor or investigator terminates the study.

If, during the trial, a participant develops non-life threatening side-effects, the study medication will be suspended if the participant insists, after consultation with a study physician. If the participant decides to stop the study medication, the participant will still be followed in the trial according to the protocol, in keeping with the

intention-to-treat paradigm. In the event of major dermatological reactions such as generalized urticaria, bullous rashes, exfoliative dermatitis, or Stevens-Johnson Syndrome, study drug will be discontinued immediately.

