Pregnancy will be managed according to the guidelines and study drug will be discontinued immediately upon discovery. For safety, a pregnancy test is done for female participants of child-bearing potential at each follow-up visit and before each GES procedure. In the event of major dermatological reactions such as generalized urticaria, bullous rashes, and exfoliative dermatitis, study drug will be discontinued immediately and not restarted. For local skin reactions, study drug may be discontinued if the skin reactions are potentially drug related. If the rashes clear, the study drug may be restarted.

Monitoring for comorbid conditions is done at each study visit through a follow-up medical history, follow-up physical exam, follow-up adverse event reports, and laboratory measures of glucose or other labs, as well as assessments of vital signs.

In addition to the medications listed in [section 6.5](#), which are exclusionary for the BESST trial, the Buspirone Investigator's Brochure does not recommend use of the drug in patients with impaired hepatic or renal function. Prospective participants with these conditions will be excluded from the trial. Most adverse events reported while taking buspirone are infrequent to rare, and are unexpected in the 4-weeks of treatment in the BESST trial.

Follow-up of Ongoing Adverse Events

Provisions for follow-up of adverse events (AE) include phone calls by the coordinators to assess symptoms, in-person follow up exams when needed to assess vital signs and physical findings and referral to local ongoing care by the PCP or hospital when needed.

The participant is queried about the adverse event until there has been a resolution of the AE. All information is recorded on the Adverse Event Report form and reviewed by the DSMB twice a year or at more frequent intervals if the DSMB determines the need. In addition, any AE with a severity grade greater than 2 is reviewed by the BESST Medical Safety Officer as soon as the event is keyed to the data system.

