8.3.3.1 SEVERITY OF EVENT

All Adverse Events (AEs) will be assessed by the study clinician and classified and graded for severity using the National Cancer Institute's Common Terminology Criteria for Adverse Events (CTCAE) version 5.0 when possible. The GpCRC Medical Safety Officer was involved in deciding which grading system to use for the GpCRC.

For AEs not included in the protocol defined grading system, the following guidelines will be used to describe severity.

- **Mild** – Events require minimal or no treatment and do not interfere with the participant's daily activities.
- **Moderate** – Events result in a low level of inconvenience or concern with the therapeutic measures. Moderate events may cause some interference with functioning.
- **Severe** – Events interrupt a participant's usual daily activity and may require systemic drug therapy or other treatment. Severe events are usually potentially life-threatening or incapacitating. Of note, the term "severe" does not necessarily equate to "serious".

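### When a participant with a treatment-related grade 3 or higher event that is not life-threatening wishes to continue, Sections 2.3.1 and 7.1 conflict on stopping study drug, and neither is given precedence

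*Combined protocol and SAP*

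**What the plan says.** Four places in the combined protocol and SAP bear directly on the point.

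- Section 7.1, for a treatment-related event graded under CTCAE v5.0: "adverse event (grade 3 or above) on the 10 mg dose, the study medication will be stopped after assessment by the site study investigator". The next sentence adds a second ground: "If in the view of the study investigator, the participant is intolerant of the medication, the participant will be withdrawn from the study medication". It carries no grade limit and does not mention what the participant wants.
- Section 2.3.1, under treatment of side effects, covers "non-life threatening side effects that may be attributed to the study drug, the study drug will be stopped only if the participant so desires". The same paragraph then names an exception: "In the event of major dermatological reactions such as generalized urticaria, bullous rashes, exfoliative dermatitis, or Stevens-Johnson Syndrome, study drug will be discontinued immediately". A later paragraph of 2.3.1 also stops the drug on pregnancy. No exception is made for grade 3 or higher events.
- Section 7.2, for side effects that are not life-threatening: "the study medication will be suspended if the participant insists, after consultation with a study physician". It repeats the dermatological exception but has no grade limit and no reference to 7.1.
- Section 8.2 provides central oversight: "any AE with a severity grade greater than 2 is reviewed by the BESST Medical Safety Officer as soon as the event is keyed". It does not say which stopping rule that officer should apply.

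Sections 2.3.1 and 7.1 both keep a participant who stops study drug in trial follow-up.

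**The concern.** Section 2.3.1 makes the participant's wish a necessary condition for stopping; Section 7.1 makes the grade and relatedness of the event sufficient after the investigator's assessment. For an event within both rules, the two agree only if the participant also wants to stop. If the participant wants to continue, an investigator at any of the six centers can cite the protocol for either action, and two centers could treat the same event differently while each believed it was compliant. Section 10.1.10 defines a deviation as noncompliance with the protocol, so in this case nobody could say whether a deviation had occurred.

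The stake is participant safety and consistent conduct. It is much less a matter of the primary result.

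**Working it through.** The point rests on wording, so the check sets the rules side by side and asks whether one event can fall under both.

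| | Section 2.3.1 | Section 7.1, first rule | Section 7.1, second rule |
|---|---|---|---|
| Trigger | Side effect, possibly due to study drug, not life-threatening | Treatment-related CTCAE event, grade 3 or above | Intolerance in the investigator's view |
| Upper severity limit | Life-threatening | None | None |
| Role of participant's wish | Necessary for stopping | Not mentioned | Not mentioned |
| Named exceptions | Major skin reactions; pregnancy | None | None |

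1. *Attribution.* An event judged treatment-related under 7.1 is also one that may be attributed to study drug under 2.3.1. The 7.1 attribution condition therefore lies inside the 2.3.1 condition.

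2. *Severity.* Section 9.4.4 classifies the highest adverse event grade as none, mild, moderate, severe or life-threatening. Severe is a separate category below life-threatening, so the plan itself recognises severe events that are not life-threatening. Reading that list in order, with none as zero, severe is the third grade, which meets the 7.1 threshold.

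3. *A passage that might close the gap.* Section 8.3.3.1 says: "Severe events are usually potentially life-threatening or incapacitating". That description applies to events outside the CTCAE grading, whereas 7.1 concerns CTCAE-defined events. It is also qualified twice, and an incapacitating event need not be life-threatening. The overlap remains.

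4. *Outcome in the overlap.* Take a treatment-related severe event that is not life-threatening and not a major skin reaction, in a participant who is not pregnant and wishes to continue. Under 7.1 the drug is stopped. Under 2.3.1 it is not, because the necessary condition is not met and no listed exception applies. Both cannot be followed.

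5. *Intolerance.* The second rule in 7.1 rests on the investigator's view alone. If the investigator finds intolerance from effects that are not life-threatening and the participant wants to continue, the same divergence from 2.3.1 follows.

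6. *Section 7.2.* It says the drug is suspended if the participant insists. It does not say that this is the only route to stopping, so it can stand alongside 7.1. It does not resolve the conflict, because it does not refer to 7.1.

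7. *Time in which the case could arise.* From Sections 1.1 and 9.2, 108 participants × 4 weeks = 432 participant-weeks in total, and 54 × 4 = 216 per arm. This is planned treatment time, not an expected number of events. The documents give no rate of treatment-related grade 3 events, so no probability is estimated.

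**The case against.** The best answer is that the two sections have different jobs. Section 2.3.1 is a risk narrative, while 7.1 is titled for discontinuation of the intervention, states a graded criterion and names who assesses it. A sensible reader would probably follow 7.1. That stands as a reading, but no section states the ranking, the wording of 2.3.1 leaves no room for an unlisted exception, and participant-led language reappears in the operative Section 7.2.

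A second argument is that side effects and adverse events are different things here. The synopsis lists them separately, the schedule of activities and Section 8.2 give them separate instruments, and severity grades attach to adverse events. This is a fair limit on how cleanly the rules overlap. It does not remove the overlap: Section 8.3.1 defines adverse events broadly, nothing caps side effects below grade 3, and restricting the 2.3.1 rule to effects that are not life-threatening implies that severe ones were in view.

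Third, physicians can stop the drug on other grounds: concomitant medication (6.5), safety at risk, in the text on comorbid conditions, and local skin reactions (both 8.2). Under 7.2 an investigator may also withdraw a participant from the study for an adverse event when continuing is not in that person's interest. These show that 2.3.1 is not a complete account of stopping, but each has its own context and none ranks 2.3.1 against 7.1.

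Fourth, 7.1 calls for the investigator's assessment first, which might be read as discretion. The consequence is nevertheless stated as definite. If discretion was intended, that would be a further rule needing to be written down.

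Finally, intolerance is undefined, so the overlap on that limb is less certain than on the grade 3 limb.

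**Conclusion.** The inconsistency is real and should be fixed. For a treatment-related event of grade 3 or higher that is not life-threatening, in a participant who wishes to continue, 2.3.1 and 7.1 give incompatible instructions. The conclusion assumes that the side effects in 2.3.1 can include graded adverse events, and that the severity list in 9.4.4 reflects the grades used in 7.1.

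The practical reach is narrow. Section 8.2 says: "Most adverse events reported while taking buspirone are infrequent to rare, and are unexpected in the 4-weeks of treatment in the BESST trial". Major skin reactions and pregnancy lie outside the conflict, and central review of events above grade 2 limits undetected differences between centers, although it supplies no rule. The effect on the intention-to-treat primary analysis is small because follow-up continues whether or not the drug is stopped.

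**What to change.** The sponsor should reconcile Section 2.3.1 with Section 7.1 so that one rule is stated, covering both the grade 3 or higher sentence and the intolerance sentence, and should add a cross-reference to 7.1 in Section 7.2. The consent text was not among the documents reviewed; if it repeats the 2.3.1 wording, it should be aligned. Which rule applies is a clinical decision for the investigators and the Medical Safety Officer, and this review does not propose one.

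The cost is one sentence in 2.3.1 or 7.1, one cross-reference in 7.2, and matching consent text if needed. Design, sample size and analysis are unaffected.
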